4.5 Maintenance of Treatment Randomization Code and Procedures for Breaking the Code

Unblinding may only occur for emergency purposes which would affect clinical care. Investigators should note that the occurrence of a serious adverse event or progressive disease

should not routinely precipitate the immediate unblinding. If unblinding is necessary for the treatment of a subject for a serious adverse event, every attempt should be made to contact the Principal Investigator (PI) prior to unblinding. If this is not feasible, then the Principal Investigator must be contacted within 24 hours of unblinding.

4.6 Early Withdrawal of Subjects

4.6.1 When and How to Withdraw Subjects

A subject may be withdrawn from the study prior to that subject completing all of the study related procedures for the following reasons.

- Unanticipated adverse effects that are possibly or probably related to the study drug
- patients who miss more than 20% of doses or are not adherent to protocol requirements.
- Disease progression
- Subject decision to withdraw from the study (withdrawal of consent)
- Liver transplantation

Subjects who withdraw from the study for safety concerns or disease progression will be included in the primary analysis (safety and tolerability). As this is a short-term study, there will be no specific clinical follow-up for subjects withdrawn from the study.

4.6.2 Data Collection and Follow-up for Withdrawn Subjects

Even though a subject has withdrawn from the study, it may be important to collect some follow-up or survival data on such subjects throughout the protocol defined follow-up period. Such data is important to the integrity of the final study analysis since early withdrawal could be related to the safety profile of the study drug in this population. If a subject withdraws consent to participate in the study, for subject safety reasons, attempts will be made to obtain permission to collect follow up information whenever possible.

5 Study Drug

5.1 Description

Letrozole is a nonsteroidal competitive inhibitor of the enzyme aromatase. By inhibiting aromatase, letrozole inhibits the conversion of androgens to estrogens. It is administered orally. The package insert is included in the IRB protocol documents.

5.2 Treatment Regimen

Subjects will take 2.5 mg of Letrozole or an identical placebo by mouth daily for 6 months.

5.3 Method for Assigning Subjects to Treatment Groups

This is a double-blinded randomized placebo-controlled trial. At the Baseline visit, subjects will be randomized to a have a code. The Research Pharmacy will receive the message and prepare the appropriate medication as assigned to the code. t

5.4 Preparation and Administration of Study Drug

Letrozole and placebo tablets will be over-encapsulated by the Research Pharmacy both at the Mayo Clinic and at the University of California, San Francisco. At the Research Pharmacy, capsules will be packaged into identical bottles with a liner, cotton, and childproof cap. Bottles will be labeled to meet state and FDA requirements. There will be two visits during which the drug will be administered. At the (Baseline), subjects will receive a 3-month supply; and at their 3 month, (Month 3) subjects will receive a 3-month supply of drug.

5.5 Subject Compliance Monitoring

Compliance will be assessed using pill logs and pill containers. Subjects will be asked to bring bottles to each study visit to allow for tracking of compliance and medication control. Non-compliant patients who miss more than 20% of doses will be asked to withdraw from the study for not complying with study protocol.

5.6 Prior and Concomitant Therapy

We will collect data regarding current prescription and non-prescription medication use.

Concomitant medications and therapies including rescue therapies are permitted. There are no contraindicated medications in the setting of letrozole use.

5.7 Masking/Blinding of Study

All study personnel and subjects will be masked for the duration of the study until the last subject completes follow-up assessments. The Research Pharmacist, statistical analyst and the DSMB will be unmasked. The Research Pharmacist will supply the statistical analyst and the DSMB with the drug/placebo identifier.

5.8 Storage of Study Drug

All study drugs prepared at the Research Pharmacy will be stored in accordance with Good Clinical Practice (GCP) and Good Manufacturing Practices (GMP) requirements and the instructions given by the clinical supplies department of the Institution and will be inaccessible to unauthorized personnel.

Regular study drug reconciliation will be performed to document drug dispensed and drug remaining. This reconciliation will be logged on the drug reconciliation form and signed and dated by the study team.

5.9 Return or Destruction of Study Drug

At the completion of the study, there will be a final reconciliation of drug dispensed and drug remaining. This reconciliation will be logged on the drug reconciliation form, signed and dated. Any discrepancies noted will be documented and investigated, prior to return or destruction of unused study drug. After accountability has been completed and notification by the research coordinator has been sent, any remaining study product at each Research Pharmacy will be destroyed. Destruction will be documented on the Drug Accountability Record Form.

6 Study Procedures

6.1 Study Visits

6.1.1 Informed Consent

Eligible subjects meeting the inclusion/exclusion criteria will be referred if there is interest in enrolling. The following procedures will be performed during the screening process:

- Sign and date the informed consent and HIPAA release
- Review of the inclusion/exclusion criteria
- Schedule a screening visit

After the subject has consented, the subject will be scheduled for a baseline visit within 60 days. If the baseline visit is not scheduled within the first 2 weeks following the informed consent, the research coordinator will send a reminder letter to the subject. The coordinator will also request that the subject refrain from smoking for 12 hours prior to the study visit. Visit 1: Baseline

Baseline information will be used to characterize the participants and to compare the experimental groups with regards to demographics and other variables. Safety laboratories, ABG, and contrast TTE obtained at the screening visit will be used as baseline measurements. Eligibility criteria will be reviewed prior to randomization to treatment group.

The research coordinator will remind the subject to avoid heavy exercise for 12 hours prior to the study visit. The coordinator will also request that the subject refrain from smoking for 12 hours prior to the study visit.

The following procedures will be performed within 60 days of consent, during the baseline visit and after evaluation of this data, the investigator will determine they are eligible to enroll in the trial:

- Review of inclusion/exclusion criteria
- Labs/Phlebotomy: complete blood count with differential, including hemoglobin, hematocrit, and platelet count, complete metabolic panel, and coagulation studies, lipid panel, estradiol, progesterone, testosterone, sample for storage for future studies; stored samples will only apply to the 10 Mayo participants. Values can be obtained from last 90 days
- Arterial blood gas (while seated while breathing room air) Values can be obtained from last 90 days.
- Spirometry and lung volumes (if not performed within the prior 3 years)
- Contrast echocardiogram. Values can be obtained from last 365 days.
- Technetium macroaggregated albumin perfusion scan Values can be obtained from last 365 days.
- DEXA scan Values can be obtained from last 365 days.
- Review of medical history
- Review current medications
- Vital signs
- Physical exam Values can be obtained from last 90 days.
- Modified Medical Research Council (mMRC) Dyspnea Scale assessment Values can be obtained from last 30 days.

- SF-36 questionnaire assessment
- 6 minute walk distance with Borg Score
- Dispense supply of study drug
- Reinforce instructions on recording of new medications and dose changes
- Reinforce instructions on bringing the subject's routine and study medications to all visits

Blood samples for study assays will be processed and/or banked.

After confirming inclusion criteria, the subject will be randomized to a treatment group using the Web-based database by the research coordinator. A pre-packaged 3 month supply of study medication (encapsulated letrozole 2.5 mg or placebo capsules) will be dispensed by the Research Pharmacy. Subjects will be instructed on the proper administration of the study medication.

Once instruction has been given to the subject and the subject expresses understanding, the research coordinator will thank the subject for their attendance and reinforce compliance with the study medication and protocol. The subject is encouraged to update their primary doctor about their medication changes.

6.1.2 Visit 2: 1 Month Visit (+/- 30 day window)

This visit may be done via telemedicine if agreed upon by both provider and study subject. Subjects will still be instructed to bring their routine and study medications with them to each visit.

The subject will arrive at the study site outpatient clinic. The following procedures will be performed:

- Interim medical history
- Vital signs (if in-clinic visit)
- Physical exam (if in-clinic visit)
- Review current medications
- Study drug accountability
- Assessment of adverse effects
- Modified Medical Research Council Dyspnea Scale assessment
- Reinforce instructions on recording of new medications and dose changes
- Reinforce instructions on bringing the subject's routine and study medications to all visits

The investigator or a nurse will take an interim medical history and perform a physical examination including vitals (if in-clinic visit), review current medications, and complete the mMRC Dyspnea Scale assessment. Coordinator or other study staff will ensure subject has enough drug to reach 3-month time point. Subjects will again be instructed on the proper administration of the study medication.

Once instruction has been given to the subject and the subject expresses understanding, the research coordinator will thank the subject for their attendance and reinforce compliance with the study medication and protocol.

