1.3 Dose Rationale

The rationale for the dose is based on typical dose regimens for other conditions (breast cancer adjuvant or primary treatment). Letrozole is only available orally. Letrozole has a half-life of 2 days and in prior pharmacokinetic studies a dose of 2.5 mg daily takes from 2-6 weeks to reach steady-state plasma concentrations.

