3.1 General Description

This study is a phase II randomized, double-blind, placebo-controlled parallel trial of 20 subjects with hepatopulmonary syndrome designed to assess the effect of letrozole 2.5 mg orally daily or placebo for 6 months on the alveolar-arterial oxygen gradient (AaPO₂).

Subjects at each site will be screened at outpatient clinic visit appointments and interested qualified subjects will be consented and offered participation in this trial. Once consent has been obtained baseline values will be established and subjects will begin letrozole with follow-up clinic visits and testing at 1 month, 3 months, and 6 months.

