6.2 Visit 3: 3 Month Visit (+/- 30 day window)

The coordinator will request that the subject refrain from smoking for 12 hours prior to the study visit.

The subject will arrive at the study site outpatient clinic. The following procedures will be performed:

- Labs/Phlebotomy: complete blood count with differential, including hemoglobin, hematocrit, and platelet count, complete metabolic panel, and coagulation studies, lipid panel, estradiol, progesterone, testosterone, sample for storage for future studies; stored samples will only apply to the 10 Mayo participants.
- Arterial blood gas (while seated while breathing room air)
- Review of medical history
- Review current medications
- Vital signs
- Physical exam
- Modified Medical Research Council Dyspnea Scale assessment
- Dispense supply of study drug (3 month supply to be given at this visit)
- Reinforce instructions on recording of new medications and dose changes
- Reinforce instructions on bringing the subject's routine and study medications to all visits

Blood samples for study assays will be processed and/or banked.

The investigator or research coordinator will take an interim medical history and perform a physical examination including vitals, review current medications, and complete the mMRC Dyspnea Scale assessment. A pre-packaged 3 month supply of study medication (encapsulated letrozole 2.5 mg or placebo capsules) will be prepared for the subject by the Research Pharmacy. Subjects will again be instructed on the proper administration of the study medication.

Once instruction has been given to the subject and the subject expresses understanding, the research coordinator will thank the subject for their attendance and reinforce compliance with the study medication and protocol. The coordinator will contact the clinician 24 hours after the study visit to discuss the clinical lab results.

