6.3 Visit 4: 6 Month Visit (+/- 30 day window)

The research coordinator will remind the subject to avoid heavy exercise for 12 hours prior to the study visit. The coordinator will also request that the subject refrain from smoking for 12 hours prior to the study visit.

The subject will arrive at the study site outpatient clinic. The following procedures will be performed:

- Labs/Phlebotomy: complete blood count with differential, including hemoglobin, hematocrit, and platelet count, complete metabolic panel, and coagulation studies, lipid panel, estradiol, progesterone, testosterone, sample for storage for future studies; stored samples will only apply to the 10 Mayo participants.
- Arterial blood gas (while seated while breathing room air)
- Technetium macroaggregated albumin perfusion scan

- Review of medical history
- Review current medications
- Vital signs
- Contrast echocardiogram
- Physical exam
- Modified Medical Research Council Dyspnea Scale assessment
- SF-36 questionnaire assessment
- 6 minute walk distance with Borg Score

Blood samples for study assays will be processed and/or banked.

After all these studies have been completed, the investigator or research coordinator will take an interim medical history and perform a physical examination including vitals, review current medications, and complete the mMRC Dyspnea Scale assessment.

The research coordinator will thank the subject for his or her participation. The coordinator will contact the clinician 24 hours after the study visit to discuss the clinical lab results.

Test	Baseline	1 month	3 months	6 months
History	X	X	X	X
Modified Medical Research Council (mMRC) Dyspnea Scale	X	X	X	X
Assessment of adverse effects-		X	X	X
Assessment of compliance		X	X	X
Physical examination, including vital signs	X	X**	X	X
Room air arterial blood gas in seated position	X		X	X
Laboratory Data*	X		X	X
SF-36	X			X
Contrast-enhanced echocardiogram	X			X
Technetium macroaggregated albumin perfusion scan	X			X
6 minute walk distance with Borg Score at baseline and completion	X			X
Complete pulmonary function tests if not performed within 3 years (spirometry, lung volumes and diffusion capacity)	X			
DEXA Scan	X			
Dispense study medication	X		X	

* Laboratory data to include complete blood count, complete metabolic panel, lipid panel, PT/INR, estradiol, progesterone and testosterone levels and stored samples for future analysis.

** If in-clinic visit

7 Assessment of Efficacy and Outcome Measures

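### The ±30-day window on the 1-month visit equals the whole interval from baseline, so the only scheduled adverse-effect and compliance check before month 3 can fall at dispensing or on the day of Visit 3

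*Combined protocol and SAP*

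**What the plan says.** Section 3.1 schedules "follow-up clinic visits and testing at 1 month, 3 months, and 6 months" and no other post-baseline contact. All three visits carry the same tolerance:

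- 6.1.2: "Visit 2: 1 Month Visit (+/- 30 day window"
- 6.2: "Visit 3: 3 Month Visit (+/- 30 day window"
- 6.3: "Visit 4: 6 Month Visit (+/- 30 day window"

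The Visit 2 procedures include "Assessment of adverse effects", drug accountability and the mMRC scale. The schedule table at the end of 6.3 marks adverse effects and compliance at months 1, 3 and 6, and laboratory data at baseline and months 3 and 6 but not month 1. On format, 6.1.2 says: "This visit may be done via telemedicine if agreed upon by both provider and study subject". Vital signs and examination are then done only if the subject attends in person.

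On exposure, 1.3 says that "a dose of 2.5 mg daily takes from 2-6 weeks to reach steady-state plasma concentrations". On supply, 5.4 says that at baseline "subjects will receive a 3-month supply; and at their 3 month, (Month 3) subjects will receive a 3-month supply of drug".

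The protocol states no minimum time on drug before Visit 2 and no minimum spacing between visits.

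**The concern.** A tolerance as wide as the interval it applies to does not define a 1-month assessment. At months 3 and 6 the same 30 days is a fraction of the time since baseline. At month 1 it is all of it.

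What is at stake is mainly early safety and adherence information. Under 9.6.1, subjects whose adverse effects are judged probably related to letrozole stop the study. Under 5.5, those who miss more than 20% of doses are asked to withdraw. Both rules depend on someone looking. A pill count in the first day or two has almost nothing to count, and an adverse-effect review at that point says little about the drug. At the other end of the window, a Visit 2 held with Visit 3 adds no early check.

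There is also a smaller data issue. Section 8.4.3 lists the mMRC scale among the outcomes for longitudinal models, so a value labelled month 1 could come from a subject with anything from 0 to 60 days of exposure.

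**Working it through.** The plan gives no figure for the spacing between visits, so there is none to reproduce. The check is arithmetic on the windows.

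**Inputs.** Nominal visits at months 1, 3 and 6 (3.1); tolerance ±30 days at each (6.1.2, 6.2, 6.3); steady state at 2 to 6 weeks (1.3); a 3-month supply at baseline (5.4). Assumptions: 30-day months, day 0 is baseline dispensing, and a 3-month supply is 90 daily capsules with no overage, since none is stated.

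**1. Windows.** Earliest = 30 × month − 30; latest = 30 × month + 30.

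| Visit | Nominal day | Earliest | Latest |
|---|---|---|---|
| 2 | 30 | 0 | 60 |
| 3 | 90 | 60 | 120 |
| 4 | 180 | 150 | 210 |

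Visit 2 reaches back to dispensing and meets Visit 3's window at day 60.

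**2. Against the steady-state figure.** 2 to 6 weeks is day 14 to day 42. Days 0 to 13, which are 14 of the 61 permitted days (23%), come before even the earliest of these. This is a share of permitted calendar days, not a forecast of when visits will happen.

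**3. Gap from Visit 2 to Visit 3.**

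- Both on the nominal day: 90 − 30 = 60 days.
- Visit 2 earliest, Visit 3 on time: 90 − 0 = 90 days.
- Visit 2 on time, Visit 3 latest: 120 − 30 = 90 days.
- Visit 2 earliest, Visit 3 latest: 120 − 0 = 120 days.
- Visit 2 latest, Visit 3 earliest: 60 − 60 = 0 days.

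**4. Sensitivity to the length of a month.** With 28-day months the longest gap is 114 days, and the two windows overlap from day 54 to day 58. With 30.44-day months the longest gap is about 121 days, Visit 2 opens at day 0.4, and the windows miss each other by less than a day (60.4 against 61.3).

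**5. Supply.** Ninety capsules last 90 days at full adherence and 90 / 0.8 = 112.5 days at 80% adherence. Both fall short of day 120.

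**6. Primary endpoint.** The 6-month AaPO₂ is measured on days 150 to 210. The latest compliant Visit 3, where the schedule table marks compliance again, is day 120, so at least 150 − 120 = 30 days separate them.

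**The case against.** The best defence is that nobody would hold a 1-month visit on day 1. Its content (an interim history, drug accountability, confirming enough drug to reach month 3) presupposes some time on treatment. Under 10.1, staff ask about adverse events whenever they are in contact with a subject, and subjects report events themselves. Under 9.3.4, serious unexpected events go to the coordinating center, usually within 24 hours. So the gap is in scheduled contact, not in all adverse-event capture. That stands. It makes the extreme dates unlikely and softens their effect, but it does not make the written window sensible.

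Several stronger readings are tempting and are not supported:

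- A reader might infer about four months on drug without a safety contact. The baseline supply may run out before day 120, so only the absence of a scheduled contact is secure.
- A reader might blame the full 120 days on Visit 2. It also needs Visit 3 at its latest. Nor is it the longest gap the windows allow: Visit 3 to Visit 4 can reach 210 − 60 = 150 days.
- A reader might infer that 6.1.2 contradicts 1.3, because 42 of the 61 permitted days (69%) precede day 42. The nominal day 30 also precedes day 42. Section 1.3 describes time to steady state and does not say that earlier exposure is uninformative.
- A reader might infer harm to the primary result. Compliance is checked again at month 3, before the 6-month AaPO₂. Missed doses that go unnoticed early could affect the secondary 3-month AaPO₂.
- A reader might infer that endpoint data at month 1 are compromised. No endpoint is set at 1 month: 3.5 compares mMRC at 6 months, and 8.7 summarizes toxicity without a month-1 cut.

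**Conclusion.** The point holds as a minor defect in the visit schedule. As written, the only scheduled adverse-effect and compliance check before month 3 can coincide with dispensing or with Visit 3, and in either case it does not serve as an early check. An earliest-date Visit 2 lengthens the wait for the next scheduled safety contact from 60 days to about 90, and to about 120 (114 to 121 across month definitions) if Visit 3 is also as late as allowed. The effect on analysis is confined to mixed exposure in the month-1 mMRC values of a secondary longitudinal model.

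This rests on counting days from baseline dispensing and on months of about 30 days. It also takes the schedule table as governing: the table marks adverse effects at months 3 and 6, although the procedure lists in 6.2 and 6.3 do not name that assessment.

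**What to change.** In 6.1.2, replace the uniform ±30 days with a narrower window specific to Visit 2, its width chosen by the sponsor, that cannot reach back to baseline and cannot meet Visit 3's window. State the day from which visits are counted. For a symmetric half-width of w days, both conditions need w below 30 (30 − w > 0 and 30 + w < 60). That is only the bare minimum. The sponsor should choose the width with the visit's purpose and the steady-state figure in 1.3 in view.

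Then reconcile 6.1.2 with 6.2, 1.3 and the dispensing plan in 5.4, so that a compliant late Visit 3 and the baseline supply are consistent, and align the schedule table with the procedure lists in 6.2 and 6.3.

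A narrower Visit 2 window does not by itself bring the longest gap down to the nominal one. With Visit 3's window unchanged, that gap is 120 − (30 − w) = 90 + w days. Whether that is acceptable is for the sponsor to decide and state.

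The cost is one changed number and a few more out-of-window deviations to log. The visit may already be done remotely, so no travel need be added. No change to dose or dosing schedule is proposed.
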